1.1. Objectives, Endpoints, and Estimands

1.1.1. Objectives and Endpoints

Changes to the protocol-planned objectives and endpoints are described in Section 4.9.

Table GPHL.1.1. Objectives and Endpoints

Objectives	Endpoints
Primary	

To demonstrate that tirzepatide 10 mg and/or 15mg QW is superior to placebo at 72 weeks for:
 
 • Percent change in body weight AND • Proportion of participants with $\geq 5\%$ body weight reduction 	
 • Mean percent change in body weight from randomization • Percentage of study participants who achieve $\geq 5\%$ body weight reduction from randomization
Key Secondary (controlled for type I error), by dose analysis	

For QW tirzepatide 10 mg and/or 15 mg doses, to demonstrate superiority to placebo in change from randomization for the following (at 72 weeks):
 
 • Body weight • Glycemic control • Waist circumference 	
 • Percentage of participants who achieve: 
 ○ $\geq 10\%$ body weight reduction ○ $\geq 15\%$ body weight reduction ○ $\geq 20\%$ body weight reduction • Mean change in HbA1c (%) • Percentage of participants who achieve: 
 ○ HbA1c $< 7\%$ ○ HbA1c $\leq 6.5\%$ ○ HbA1c $< 5.7\%$ • Mean change in fasting glucose (mg/dL) • Mean change in waist circumference (cm)

Objectives	Endpoints
Key secondary (controlled for type I error), pooled dose analysis	

For QW tirzepatide (all doses combined), to demonstrate superiority to placebo in change from randomization for the following (at 72 weeks):
 
 • Lipid parameters • SBP 	
 • Mean change in fasting 
 ○ Triglycerides (mg/dL) ○ HDL-cholesterol (mg/dL) ○ Non-HDL-cholesterol (mg/dL) • Mean change in SBP (mmHg)
Additional Secondary, by dose analysis	

For QW tirzepatide 10 mg and/or 15 mg doses, to demonstrate superiority to placebo in change from randomization for the following (at 72 weeks):
 
 • Body weight • 7-point self-monitored blood glucose profiles • Insulin • Patient-Reported Outcomes 	
 • Mean change in absolute body weight (kg) • Mean change in BMI (kg/m²) • Mean change in 
 ○ each of the 7-point measurements ○ 2-hour morning, midday and evening meal excursions, and all meals 2-hour excursion ○ mean of all 7-point measurements, mean of all pre-meal measurements, and mean of all 2-hour postprandial measurements • Mean change in fasting insulin (pmol/L) • Mean change in 
 ○ SF-36v2 acute form Physical Functioning domain score ○ IWQOL-Lite-CT Physical Function composite score ○ EQ-5D-5L utility score and VAS score

Objectives	Endpoints
Additional Secondary, pooled analysis	

For QW tirzepatide (all doses combined), to demonstrate superiority to placebo in change from randomization for the following (at 72 weeks):
 
 • Lipid parameters • DBP 	
 • Mean change in fasting 
 ○ Total cholesterol (mg/dL) ○ LDL-cholesterol (mg/dL) ○ VLDL-cholesterol (mg/dL) ○ Free fatty acids (mg/dL) • Mean change in DBP (mmHg)

Abbreviations: BMI = body mass index; DBP = diastolic blood pressure; HbA1c = hemoglobin A1c; HDL = high-density lipoprotein; IWQOL-Lite-CT = Impact of Weight on Quality of Life-Lite-Clinical Trials Version; LDL = low-density lipoprotein; QW = once weekly; SBP = systolic blood pressure; SF-36v2 acute form = Short Form-36 Health Survey version 2 acute form; VAS = Visual Analog Scale; VLDL = very low-density lipoprotein.

1.1.2. Estimands

1.1.2.1. Estimands for Co-primary Endpoints

The primary clinical question of interest is: What is the intervention difference between QW tirzepatide 10 mg and/or 15 mg and placebo in mean percent change in body weight and proportion of participants who achieve $\geq 5\%$ body weight reduction from randomization to 72 weeks in participants with T2DM, who have obesity (BMI ≥ 30 kg/m²) or overweight (BMI ≥ 27 kg/m²)?

For primary disclosure of Study GPHL including submission to the US Food and Drug Administration (FDA)

The estimand is described by the following attributes:

- Population: all randomized participants who received at least 1 dose of study drug.
- Co-primary endpoints: mean percent change, from randomization to Week 72, in body weight, AND percentage of study participants who achieve $\geq 5\%$ body weight reduction from randomization to Week 72.
- Treatment condition of interest: tirzepatide 10 mg and/or 15 mg versus placebo, regardless of study drug adherence.
- Handling of intercurrent events: the intercurrent event leading to treatment discontinuation for any reason is addressed by the treatment condition of interest attribute and handled by treatment policy strategy as described in ICH E9 (R1) Addendum (ICH 2019). Further details can be found in Section 4.3.2.1.

- Population-level summary: difference in mean changes between treatment conditions, AND difference in response percentage between treatment conditions as assessed by odds ratio.

Rationale for estimand: It aims to reflect treatment effect among participants with T2DM and with obesity or overweight, irrespective to the compliance to the planned course of treatment.

This *de facto estimand* is referred to as the “treatment regimen” estimand in the latter sections of this document, which is equivalent to the “hybrid” estimand as stated in the protocol.

For other purposes

The estimand is described by the following attributes:

- Population: all randomized participants who received at least 1 dose of study drug.
- Co-primary endpoints: mean percent change from randomization to Week 72 in body weight, AND percentage of study participants who achieve $\geq 5\%$ body weight reduction from randomization to Week 72.
- Treatment condition of interest: tirzepatide 10 mg and/or 15 mg versus placebo, excluding data after discontinuation of study drug.
- Handling of intercurrent events: the intercurrent event leading to treatment discontinuation for any reason is addressed by the treatment condition of interest attribute and handled by the hypothetical strategy as described in ICH E9 (R1) Addendum (ICH 2019).
- Population-level summary: difference in mean changes between treatment conditions, AND difference in response percentage between treatment conditions as assessed by odds ratio.

Rationale for estimand: the estimand aims to reflect treatment efficacy in an envisaged scenario in which the intercurrent events leading to treatment discontinuation would not occur.

We will refer to this estimand as “efficacy” estimand in the latter sections.

1.1.2.2. Estimands for Secondary Endpoints

Table GPHL.1.2. Attribute Description of Estimands for Secondary Endpoints

[figure not shown]
Estimand for Secondary Endpoints	Population	Endpoint	Treatment condition of interest	Handling of intercurrent events	Population-level summary
Key secondary related to mean change	Same as estimands for co-primary endpoints	As described in Table GPHL.1.1	For primary disclosure of study GPHL including submission to the US FDA, follow the same manner of the treatment regimen estimand in Section 1.1.2.1; for all other purposes, follow the same manner of the ‘efficacy’ estimand in Section 1.1.2.1	For primary disclosure of study GPHL including submission to the US FDA, follow the same manner of the treatment regimen estimand in Section 1.1.2.1; for all other purposes, follow the same manner of the ‘efficacy’ estimand in Section 1.1.2.1	Difference in mean changes between treatment conditions
Key secondary related to percentage of participants meeting certain criteria					Difference in percentage of participants between treatment conditions as assessed by odds ratio
Other secondary related to mean change	Same as estimands for co-primary endpoints	As described in Table GPHL.1.1	Follow the same manner of the ‘efficacy’ estimand in Section 1.1.2.1	Follow the same manner of the ‘efficacy’ estimand in Section 1.1.2.1	Difference in mean changes between treatment conditions

Abbreviation: FDA = Food and Drug Administration.

Unless otherwise specified, the attributes of estimands supporting exploratory objectives will follow the same manner of the efficacy estimand in Section 1.1.2.1.

1.2. Study Design

Study I8F-MC-GPHL (GPHL; SURMOUNT-2) is a Phase 3, multicenter, randomized, placebo-controlled, double-blinded study of the safety and efficacy of 10 mg and 15 mg tirzepatide QW, compared with placebo, when used in conjunction with a reduced-calorie diet and increased physical activity for weight management, in participants who have T2DM, and have obesity (BMI ≥ 30 kg/m²) or overweight (BMI ≥ 27 kg/m²). All participants will be randomized to 72 weeks of treatment to study the effects on body weight reduction.

Abbreviations: QW = once weekly; T = telephone visit.

Note: All participants will be randomized to 72 weeks of treatment to study the effects on body weight reduction. The safety follow-up visit will occur 4 weeks after participants discontinue or complete the treatment.

Figure GPHL.1.1. Illustration of study design for Clinical Protocol I8F-MC-GPHL.

The details about the overview of study periods and study visits can be found in Study GPHL protocol Section 4. The detail of the unique visits not displayed in Figure GPHL.1.1 is provided below.

Visit 99

Visit 99 is only applicable to participants who discontinue the study treatment prematurely prior to Visit 21 (Week 72). Participants will be asked to return for Visit 99 at 72 weeks \pm 7 days after randomization. This visit is critical to ensure complete data collection for the primary weight-reduction endpoint.

Participants should attend this visit in the fasting state. Procedures to be completed include

- measurement of weight and waist circumference
- concomitant medications
- assessment of AEs, and
- completion of the mental health questionnaires (after the AE assessment).

Early Discontinuation of Treatment Visit

Participants unable or unwilling to continue the study treatment for any reason will perform early discontinuation of treatment visit at the visit when the participant informs the site about the study treatment discontinuation.

[figure not shown]
2. Statistical Hypotheses

The alternative hypothesis for the primary objective and key secondary objectives are the following:

- $H_{15,1}$ and $H_{10,1}$: superiority of tirzepatide 10 mg and/or 15 mg versus placebo for mean percent change in body weight from randomization and percentage of participants who achieve $\geq 5\%$ body weight reduction at 72 weeks.
- $H_{15,2}$ and $H_{10,2}$: superiority of tirzepatide 10 mg and/or 15 mg versus placebo for percentage of participants who achieve $\geq 10\%$ body weight reduction from randomization at 72 weeks
- $H_{15,3}$ and $H_{10,3}$: superiority of tirzepatide 10 mg and/or 15 mg versus placebo for percentage of participants who achieve $\geq 15\%$ body weight reduction from randomization at 72 weeks
- $H_{15,4}$ and $H_{10,4}$: superiority of tirzepatide 10 mg and/or 15 mg versus placebo for percentage of participants who achieve $\geq 20\%$ body weight reduction from randomization at 72 weeks
- $H_{15,5}$ and $H_{10,5}$: superiority of tirzepatide 10 mg and/or 15 mg versus placebo for change from randomization in waist circumference (cm) at 72 weeks
- $H_{15,6}$ and $H_{10,6}$: superiority of tirzepatide 10 mg and/or 15 mg versus placebo for change from randomization in HbA1c (%) at 72 weeks
- $H_{15,7}$ and $H_{10,7}$: superiority of tirzepatide 10 mg and/or 15 mg versus placebo for percentage of participants who achieve HbA1c $< 7\%$ at 72 weeks
- $H_{15,8}$ and $H_{10,8}$: superiority of tirzepatide 10 mg and/or 15 mg versus placebo for percentage of participants who achieve HbA1c $\leq 6.5\%$ at 72 weeks
- $H_{15,9}$ and $H_{10,9}$: superiority of tirzepatide 10 mg and/or 15 mg versus placebo for percentage of participants who achieve HbA1c $< 5.7\%$ at 72 weeks
- $H_{15,10}$ and $H_{10,10}$: superiority of tirzepatide 10 mg and/or 15 mg versus placebo for change from randomization in fasting glucose at 72 weeks
- $H_{p,11}$: superiority of tirzepatide (all doses combined) versus placebo for change in SBP (mmHg) from randomization at 72 weeks
- $H_{p,12}$: superiority of tirzepatide (all doses combined) versus placebo for change in triglycerides (mg/dL) from randomization at 72 weeks
- $H_{p,13}$: superiority of tirzepatide (all doses combined) versus placebo for change in non-HDL-cholesterol (mg/dL) from randomization at 72 weeks
- $H_{p,14}$: superiority of tirzepatide (all doses combined) versus placebo for change in HDL-cholesterol (mg/dL) from randomization at 72 weeks

2.1. Multiplicity Adjustment

For primary and key secondary efficacy objectives, the details of type I error control strategy are illustrated in [Figure GPHL.2.1](#). Both efficacy estimand and treatment regimen estimand will be used to assess these objectives. As they are intended for different purposes, no multiplicity adjustments will be made for conducting separate analyses relative to the efficacy and treatment regimen estimands. In addition, no multiplicity adjustments will be made for evaluating other secondary and exploratory objectives, or for safety assessments.

Abbreviations: FG = fasting glucose; H = hypothesis; HbA1c = hemoglobin A1c; HDL-C = high-density lipoprotein cholesterol; Non-HDL-C = non high-density lipoprotein cholesterol; p = pooled dose; SBP = systolic blood pressure; WC = waist circumference; WL = weight loss.

Figure GPHL.2.1. Type 1 error control strategy for primary and key secondary efficacy endpoints.

3. Analysis Sets

For purposes of analysis, the following populations are defined:

Table GPHL.3.1. Description of Analysis Datasets

Population	Description
Entered	All participants who sign informed consent
Randomized	All participants who are randomly assigned a study drug.
Modified Intent-to-Treat (mITT)	All randomly assigned participants who are exposed to at least 1 dose of study drug. Participants will be included in the treatment group to which they were randomized.
Efficacy Analysis Set (EAS)	For glycemic control related endpoints: Data obtained during treatment period from mITT, excluding data after initiation of rescue antihyperglycemic medication or premature discontinuation of study drug (last dose date + 7 days). For other endpoints: Data obtained during treatment period from mITT, excluding data after premature discontinuation of study drug (last dose date + 7 days).
Full Analysis Set (FAS)	Data obtained during treatment period from mITT, regardless of adherence to study drug or initiation of rescue antihyperglycemic medication.
Safety Analysis Set (SS)	Data obtained during the treatment period plus safety follow-up period from mITT, regardless of adherence to study drug or initiation of rescue antihyperglycemic medication.

Unless otherwise specified, for analyses guided by the treatment regimen estimand, the FAS will be used; for analyses guided by the efficacy estimand, the EAS will be used; for safety analysis, the SS will be used.

4. Statistical Analyses

4.1. General Considerations

Statistical analysis of this study will be the responsibility of Lilly or its designee. Some analyses and summaries described in this analysis plan may not be conducted if not warranted by data (eg, few events to justify conducting an analysis). Additional analyses of the data may be conducted as deemed appropriate.

Unless otherwise noted, tests of treatment effects will be conducted at a 2-sided alpha level of 0.05, and the CI will be calculated at 95% 2-sided.

Unless specified otherwise, efficacy and safety will be assessed using the mITT population, and data will be analyzed based on the assigned treatment (ie, not the actual treatment received by the participant).

Summary descriptive statistics for continuous measures will include sample size, mean, SD, median, minimum, and maximum. The analysis model to make comparisons among treatment groups relative to continuous measurements assessed over time will be either ANCOVA or a MMRM.

Kaplan-Meier method will be used for estimation of cumulative event-free survival rates over time, and Cox proportional hazards regression analysis will be used to compare hazards rates among treatments.

Summary statistics for categorical measures (including categorized continuous measures) will include sample size, frequency, and percentages. Logistic regression will be used to examine the treatment difference in binary efficacy outcomes if there is a need to adjust for covariate. Otherwise, Fisher's exact test will be used to examine the treatment difference.

Summary statistics for discrete count measures will include sample size, mean, SD, median, minimum, and maximum.

Unless specified otherwise, baseline will be defined as the last available nonmissing measurement during Visit 1 to Visit 3. For the safety-related parameters, the definition of baseline and postbaseline are specified in [Table GPHL.4.1](#).

Table GPHL.4.1. Baseline and Postbaseline Definitions for Safety Groups

Analysis Set	Analysis Type	Baseline	Postbaseline
SS	(1.1) Treatment-Emergent Adverse Events	The baseline period is defined as the start of screening and ends prior to the first dose of study treatment (typically at Week 0).	Starts after the first dose of study treatment and ends at the end of the study period (including off-drug follow up visit).
SS	(1.2) Treatment-Emergent Abnormal Labs ^a , Vital Signs, and ECGs.	Baseline will include all scheduled and unscheduled measurements during the baseline period (Visit 1 to Visit 3)	Postbaseline will be defined as measurements after Visit 3. All scheduled and unscheduled measurements will be included.
SS	(1.3) Change from Last Baseline to Week xx and to Last Postbaseline for Labs ^a , Vital Signs, and ECGs.	The last scheduled and unscheduled non-missing assessment recorded during the baseline period defined above (1.2).	Postbaseline will be defined as above (1.2). Only scheduled visits will be included. The ED visits are considered scheduled visits.

Abbreviations: ECGs = electrocardiogram; ED = early discontinuation; SS = Safety Analysis Set.

^a Immunogenicity related analysis is specified in Section 4.6.5.5.

For the primary and key secondary efficacy endpoint analyses subject to type 1 error rate control, data for participants with missing values at the 72-week visit will be imputed based on the method described in Section 4.3.2.3. Otherwise, missing values will not be explicitly imputed except for the parameters with only 1 postbaseline measure during the analysis period per schedule of activity, where last observation carried forward (LOCF) approach will be applied to impute the endpoint when early discontinuation measure is available.

End of study participation for a participant will be the earliest of date of death, date of withdrawal from further participation in the study, or date of safety follow-up visit (Visit 801). For participants considered to be lost-to-follow-up, end of study participation will be the date of lost-to-follow-up reported by the investigator. Participant data included in the database after the last date of study participation (including safety follow-up period) will be excluded from statistical analysis.

Statistical treatment comparisons will only be performed between tirzepatide and placebo. Since the trial is not adequately powered to detect differences among tirzepatide doses, comparisons among tirzepatide doses will not be performed unless otherwise specified.

Statistical summaries and results of statistical analyses will be displayed in the following order: placebo, tirzepatide 10 mg, tirzepatide 15 mg, and pooled tirzepatide (all doses combined) if necessary.

Not all analyses described in this SAP will necessarily be included in the CSRs. Any analysis described in this SAP and not provided in the CSR would be available upon request. Not all displays will necessarily be created as a “static” display. Some may be incorporated into interactive display tools instead of or in addition to a static display.

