4.1.1.3. Safety Follow-up Period

Visit 801

All participants are required to complete a safety follow-up visit (Visit 801), according to the SoA. Participants discontinuing the study early and performing an ED visit will also be asked to perform the safety follow-up visit. During the safety follow-up period, participants will not receive study drug. Participants may be treated with another glucose-lowering intervention at the discretion of the investigator or participant's usual diabetes care physician (see Section 6.5.2). If any new AHM is initiated during the safety follow-up period, it will not be classified as rescue

therapy (see Section 6.5.3.1). Participants are also required to return any remaining study diaries to the study site at the end of this period.

For participants who discontinue or complete the study, Visit 801 (safety follow-up visit) should be performed 4 weeks after the last visit of the treatment period (Visit 21 or 99) or 4 weeks after the ED visit for those who decline to return for Visit 99.

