8.9. Immunogenicity Assessments

Where local regulations and ERBs allow, blood samples for immunogenicity testing will be collected to determine antibody production against tirzepatide as specified in the SoA (Section 1.3).

For immunogenicity testing, venous blood samples will be collected from each participant according to the SoA (Section 1.3) to determine antibody production against tirzepatide. To interpret the results of immunogenicity, a venous blood sample will be collected at the same time points to determine the plasma concentrations of tirzepatide. All samples for immunogenicity should be taken predose when applicable and possible.

In the event of systemic drug hypersensitivity reactions (immediate or nonimmediate), additional unscheduled samples should be collected as detailed in Section 8.3.2.7 (Hypersensitivity Reactions). Instructions for the collection and handling of blood samples will be provided by the sponsor. The actual date and time (24-hour clock time) of each sampling will be recorded. Sample collected at Visit 801 will assess immunogenicity at washout of tirzepatide (5 half-lives post end of treatment).

Immunogenicity will be assessed by a validated assay designed to detect ADAs in the presence of tirzepatide at a laboratory approved by the sponsor. Antibodies may be further characterized for their ability to neutralize the activity of tirzepatide on GIP and GLP-1Rs. Positive tirzepatide ADA samples will be tested for cross-reactivity with native GIP and GLP-1, and, if positive, may then be tested for neutralizing antibodies against native GIP and/or GLP-1. In vivo laboratory indicators for effect on weight loss and PK will be utilized to detect potential neutralizing effect of ADAs against tirzepatide.

Treatment-emergent ADAs are defined in Section 9.4.6.

Samples will be retained for a maximum of 15 years after the last participant visit, or for a shorter period if local regulations and ERBs allow, at a facility selected by the sponsor. The duration allows the sponsor to respond to future regulatory requests related to tirzepatide. Any samples remaining after 15 years will be destroyed.

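### Row (1.3) of SAP Table GPHL.4.1 lets the off-drug Visit 801 supply the Last Postbaseline value for labs, vital signs and ECGs, so that one summary probably dilutes effects that follow exposure

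*SAP*

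**What the plan says.** SAP Section 4.1, Table GPHL.4.1, sets baseline and postbaseline windows for the safety analyses. Row (1.3) is labelled "Change from Last Baseline to Week xx and to Last Postbaseline for Labs" and also covers vital signs and ECGs. Its postbaseline entry is "Postbaseline will be defined as above (1.2). Only scheduled visits will be included. The ED visits are considered scheduled visits". Row (1.2), from which it borrows, says "Postbaseline will be defined as measurements after Visit 3. All scheduled and unscheduled measurements will be included".

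The analysis set for both rows is the SS. SAP Section 3, Table GPHL.3.1, describes it as "Data obtained during the treatment period plus safety follow-up period from mITT, regardless of adherence to study drug".

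On Visit 801, Protocol Section 4.1.1.3 requires the visit of all participants and states "During the safety follow-up period, participants will not receive study drug". The same section lets other glucose-lowering treatment begin in that period. Protocol Section 8.9 describes the drug status at the visit: "Sample collected at Visit 801 will assess immunogenicity at washout of tirzepatide (5 half-lives post end of treatment". Protocol Section 4.2 gives the follow-up period the purpose of observing what happens when study drug stops. The Schedule of Activities (Protocol Section 1.3) marks vital signs, ECG, HbA1c, chemistry and most other central laboratory tests at Visit 801.

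**The concern.** Each definition is reasonable alone, but together they let a visit designed to observe drug withdrawal supply the last value. Row (1.3) removes unscheduled measurements and keeps ED visits. It is silent on Visit 801, which is scheduled, and no other SAP text takes it out. A programmer following the table would select Visit 801 for everyone who attends it.

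Elsewhere the SAP does draw the line. Section 4.6.5.3.3 reports liver enzyme elevations for the treatment period and for the entire study. Sections 4.6.5.5.2 and 4.6.5.5.4 split immunogenicity in the same way. Section 4.6.3.6 limits the model for selected labs to the treatment period. Row (1.1) of Table GPHL.4.1 names the off-drug visit when it means to include it.

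What is at stake is the direction of error in a safety summary. For a measure that tracks drug exposure, an off-drug last value moves the treatment difference toward zero. Glucose-related labs at Visit 801 may also reflect new treatment started during follow-up.

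**Working it through.** No sample size, power or alpha figure is involved. The check has three parts: which visit the definitions select, how much drug remains at that visit, and how many participants are affected.

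**1. Which visit is selected**

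| Step | Source | Result |
|---|---|---|
| Data available | SS, SAP Table GPHL.3.1 | Treatment period plus safety follow-up |
| Start of window | Row (1.2), reused by row (1.3) | After Visit 3 |
| End of window | Rows (1.2) and (1.3) | None stated |
| Removed by row (1.3) | Row (1.3) | Unscheduled measurements only |
| Latest scheduled visit | Protocol Sections 1.3 and 4.1.1.3 | Visit 801, required of all |

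For a completer who attends it, the last scheduled measurement is therefore Visit 801, not Visit 21. Hematology is a possible exception: its marks in the text version of the schedule may be shifted by a column, so I do not rely on it.

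**2. Drug remaining at Visit 801**

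- Plan's own figure: 5 half-lives after end of treatment (Protocol Section 8.9), so the remaining fraction is 2^-5 = 3.1%.
- Independent check: Protocol Section 5.1 equates 5 half-lives plus 90 days with 4 months after the last injection. Four months is about 120 to 122 days, so 5 half-lives is about 30 to 32 days and one half-life is about 6.0 to 6.4 days.
- Time off drug: Visit 801 falls 4 weeks after the last treatment-period visit. That is 28 days after the last dose if the dose coincided with that visit, and 35 days if it was a week earlier.
- Formula: remaining fraction = 2^-(days off drug / half-life).

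| Days since last dose | Half-lives elapsed | Exposure remaining |
|---|---|---|
| 28 | 28/6.4 to 28/6.0 = 4.4 to 4.7 | 4.8% to 3.9% |
| 35 | 35/6.4 to 35/6.0 = 5.5 to 5.8 | 2.3% to 1.8% |

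The stated 5 half-lives lies inside this range. With the ±3-day window on Visit 801, the extremes are 25 days (5.6% to 6.7% remaining) and 38 days (1.2% to 1.6%). The reading of Visit 801 as essentially off drug holds throughout.

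**3. Share of participants affected**

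The planning dropout is 25% (SAP Section 5), so 1 - 0.25 = 75% would complete and be due at Visit 801. If dropout were 10% or 40% (assumed range), the share would be 90% or 60%. Participants who stop drug early are also asked to attend, so the true share may be higher.

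**What the check does not give.** Step 2 concerns exposure, not response. The documents give no rate at which pulse, PR interval, pancreatic enzymes, calcitonin or any other measure reverts after the drug is stopped.

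**The case against.** The best defence is that little depends on this row. Last Postbaseline is named only in the row (1.3) label. The sections that specify the analyses work by visit:

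- **Vital signs (SAP Section 4.6.3.4):** summaries at each scheduled visit, with mean change from the Section 4.6 MMRM, which has a treatment-by-visit term.
- **ECGs (Section 4.6.3.5) and labs (Section 4.6.3.6):** summaries by nominal visit.
- **Pancreatic enzymes, calcitonin and eGFR:** maximum or minimum postbaseline categories, with by-visit summaries or MMRM.

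Section 4.1 adds that not every planned analysis need appear in the CSR. Including follow-up in the SS is also deliberate: Protocol Section 9.4.4 sets safety assessment irrespective of adherence.

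The point about reach stands. A reader might infer that the definition conceals an effect present at Week 72. The documents do not support that, because Week 72 is reported as its own visit. Nor do they show that the problem reaches a treatment comparison. Section 4.6 falls back to ANCOVA where an MMRM is not warranted, without saying which postbaseline value is used, but it does not say that the last value is used.

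The point about the SS does not settle the matter. Disregarding adherence means keeping values from participants who stopped drug during the treatment period. It does not require that completers be represented by a visit at which everyone is off drug by design.

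**Conclusion.** The point holds, with a narrow reach. As written, row (1.3) selects Visit 801 for most participants, and the change-to-last-postbaseline summary then describes status about 4 weeks off drug. For effects that follow exposure this probably dilutes the difference from placebo. By-visit summaries including Week 72, MMRM analyses, the treatment-period model for selected labs and the maximum/minimum treatment-emergent analyses do not depend on it. No efficacy result is touched.

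Two stronger readings should be resisted. One is that the summary measures washout instead of drug effect. Exposure has largely gone, but responses may not have: changes sustained by retained weight loss, for example, could persist. The other is a numerical loss obtained by multiplying an assumed on-treatment difference, such as a few beats per minute in pulse, by the remaining 2% to 5%. That needs both an effect size and a proportional link to exposure, and the documents supply neither.

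The conclusion rests on reading rows (1.2) and (1.3) literally and on participants attending the required visit. The 75% share also rests on the planning dropout. If the sponsor already intends a treatment-period last value, the SAP does not say so.

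**What to change.** In SAP Table GPHL.4.1 row (1.3), define Last Postbaseline as the last scheduled value within the treatment period: up to Visit 21, or the last treatment-period or ED visit for participants without Visit 21. Apply this regardless of adherence. Summarise change from baseline to Visit 801 in a separate follow-up row. Leave row (1.2) unchanged.

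Do not add a cut at last dose plus 7 days. That is the Efficacy Analysis Set rule. Here it would drop values from participants who stop drug but keep attending, and any ED value taken more than 7 days after the last dose, although row (1.3) expressly keeps ED visits.

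The cost is one sentence in the SAP and one derivation flag. No new data are needed, the Visit 801 information is kept, and sample size, power and alpha do not change.
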